6.1 Changes from Protocol

 Protocol Amendment version 5.0 Section 8.2: the definition of PPS is more clearly defined as all subjects in the FAS who do not have any important protocol deviations during the 24-week treatment period that would potentially affect the efficacy of the study drug.

 Protocol Amendment version 5.0 Section 8.4.2 states that "Abnormal laboratory values will be listed by subject and summaries of the incidence and frequency by treatment group, scheduled visit, severity, and relationship to IMP will be presented." Clinically significant abnormalities will be recorded as an adverse event (AE) and the severity/relationship to investigational medicinal product (IMP) will be recorded on the AE CRF page. However specific summaries of other abnormal laboratory values will not contain the assessment of relationship to the IMP or severity as this will not be collected in the laboratory database.

7.0 Study Objectives

7.1 Primary Objective

• To evaluate the effect of setanaxib on ALP at Week 24 in patients with PBC and with elevated liver stiffness and intolerance or inadequate response to ursodeoxycholic acid (UDCA)

7.2 Secondary Objectives

- To evaluate the effect of setanaxib on fatigue at Week 24
- To evaluate the effect of setanaxib on liver stiffness at Week 24
- To evaluate the effect of setanaxib on ALP, fatigue and liver stiffness at Week 24, where setanaxib doses are combined
- To evaluate the effect of setanaxib on pruritus at Week 24
- To evaluate the effect of setanaxib on markers of cholestasis at Week 24
- To evaluate the safety and tolerability of setanaxib over a 24-week treatment period

7.3 Exploratory Objectives

- To evaluate the effect of setanaxib over a 24-week treatment period on markers of liver fibrosis, cholestasis, bile acid metabolism, and liver function
- To evaluate the effect of setanaxib on adverse clinical outcomes
- To further evaluate the effect of setanaxib on patient-reported outcomes
- To determine the pre-dose plasma levels of setanaxib and its metabolite GKT138184

8.0 Study Design

This revised study is a randomized, placebo-controlled, double-blind, parallel-group, multicenter, Phase 2b study assessing oral setanaxib administered as an add-on therapy in subjects with PBC, elevated liver stiffness, and intolerance or inadequate response to UDCA. Intolerance to UDCA is defined as subjects unable to tolerate the full-labelled dose of UDCA in PBC (13-15 mg/kg) due to frequently reported gastrointestinal symptoms such as diarrhoea and abdominal pain. The safety and efficacy of 1200 mg/day and 1600 mg/day setanaxib will be assessed against matching placebo over up to 24 weeks of treatment. It is planned to enroll 60-70 subjects at approximately 80 to 130 investigational centers in North America, Europe, Israel, Australia, and New Zealand.

Subjects enrolled under previous versions (1.0 to 4.0) of the protocol were eligible to receive 52 weeks of treatment in the randomized "Main Part" of the study and then consented to a further 52 weeks of treatment

Version Date: 27-June-2024

[figure not shown]
Sponsor: Calliditas Therapeutics Suisse SA

Protocol No: GSN000350

with setanaxib in the open-label "Extension Phase". The SAP will describe how additional data already collected beyond the 24-week treatment period will be summarized.

The study design is outlined in **Figure 1**. For the schedule of assessments, refer to Table 1 in the Protocol Amendment version 5.0.

Figure 1: Study Design

EoT=End-of-Treatment: V=Visit

- ^a The Independent data monitoring committee (IDMC) may recommend change(s) to the setanaxib dose regimen(s), or interruption or discontinuation of an active treatment group(s) based on the regular IDMC safety data reviews (as defined in the IDMC Charter).
- ^b Eligible subjects will be randomized to oral setanaxib 1200 mg/day, 1600 mg/day, or placebo, according to a 1:1:1 randomization ratio.
- ^c Subjects who permanently discontinue IMP prior to Week 24 Visit (Visit 8) will have an EoT Visit 30 days after the last IMP dose, after which every possible effort should be made to complete the Week 24 Visit (Visit 8).

The study will consist of a 4-week Screening Period, a 24-week Double-blind Treatment Period, and a 4-week Follow-up Period. Under protocol version 5.0 (or later), the total duration of the study for subjects remaining in the study until their final follow-up assessment (end of treatment [EoT] visit 30 days after last investigational medicinal dose [IMP]) will be approximately 32 weeks (approximately 8 months). No interim analyses will be conducted. Unblinded safety data will be summarized by the unblinded programming team for the IDMC, for the purposes of ongoing safety review.

Eligible subjects will be randomized to oral setanaxib 1200 mg/day, 1600 mg/day, or placebo, according to a 1:1:1 randomization ratio, stratified by Screening serum ALP < or ≥3.0×ULN. Refer to Section 8.2 for further details on the randomization in this study.

Baseline assessments will be performed on Day 1 (Visit 3). Post-baseline assessments will be performed at Weeks 2 (Visit 4), 4 (Visit 5), 8 (Visit 6), 12 (Visit 7), and 24 (Visit 8). In addition, study subjects will be contacted by phone by the study site staff at Weeks 16 and 20.

Following permanent IMP discontinuation at any time during any part of the study, subjects will undergo an EoT Visit 30 days after their last dose. If IMP is permanently discontinued the study assessments should

Version Date: 27-June-2024

Sponsor: Calliditas Therapeutics Suisse SA

Protocol No: GSN000350

continue until completion of the Week 24 Visit (Visit 8). If it is not feasible to complete all the visits, every possible effort should be made to complete the Week 24 Visit.

The Investigator, the site personnel, the Sponsor and their representatives involved in monitoring and conducting the study, and the subjects will be blinded to treatment assignments until the database is locked and the study is unblinded for analysis.

The IDMC will oversee the safety of participating subjects (see Protocol Amendment version 5.0 Section 9.4.2). The role and responsibilities of the IDMC have been outlined in an IDMC Charter. An Adjudication Committee, who will remain blinded to subject treatment assignment, will adjudicate events requiring IMP interruption as per protocol and the adverse clinical outcomes (see Protocol Amendment version 5.0 Section 9.4.1). The roles and responsibilities of the Adjudication Committee are outlined in an Adjudication Charter.

8.1 Sample Size Considerations

The primary efficacy endpoint is the change in ALP (%) over 24 weeks. It is planned to enroll approximately 60 to 70 subjects. Subjects will be randomized and allocated to placebo, setanaxib 1200 mg/day, or setanaxib 1600 mg/day according to a 1:1:1 randomization ratio.

This study is designed to detect a >25% reduction in ALP in setanaxib-treated subjects versus a 2.5% reduction in the placebo arm with an overall 2-sided p<0.05. Standard deviations are assumed to be 19% and 24%, respectively, based on the Phase 2a study with setanaxib and the Phase 3 POISE study with Ocaliva. With approximately 16 evaluable subjects per arm (48 subjects overall) and using a Hochberg step-up procedure (Benjamin and Hochberg, 1995; Section 12.5.1 for details) to control alpha across 2 dose comparisons versus placebo, this study has 88.2% global power to detect at least 1 treatment arm as significantly different from placebo and 68.3% power to detect both treatment arms as statistically significant. Also, for the secondary endpoint of change in fatigue, there will be >80% power to detect a 20% (SD 20%) reduction in fatigue versus a 2.5% (23%) increase in the placebo arm.

An assumed dropout rate of approximately 25% leads to a target sample size of 66 enrolled subjects (22 per arm). A range of approximately 60 to 70 enrolled subjects allows for variability in the assumed dropout rate.

8.2 Randomization

The randomization schema remains unaffected by Protocol Amendment version 5.0. Eligible subjects enrolled according to Protocol Amendment version 5.0 will be randomly assigned to oral setanaxib 1200 mg/day, 1600 mg/day, or placebo, according to a 1:1:1 randomization ratio, stratified by Screening serum ALP < or ≥3.0×ULN.

Randomization will be performed via a centralized Interactive Web Response System (IXRS) contracted through Almac. At registration, the IXRS will assign a unique subject identification number that will be used on all of the subject's eCRFs and serious adverse event (SAE) report forms. If a subject is rescreened (see Protocol Amendment version 5.0 Section 4.3), the rescreened subject should be assigned a new unique screening number.

Any subjects who entered the Extension Phase under protocol versions 1.0 to 4.0 will have received the same setanaxib treatment dose they received during the first 52 weeks of study treatment (the Main Part). Subjects initially randomized to placebo will have been switched to setanaxib 1200 mg/day or 1600 mg/day according to a 1:1 randomization ratio in the Extension Phase. Randomization in the Extension Phase was not stratified. All subjects will have had a new randomization number assigned on enrollment into the Extension Phase, even if they were not re-randomized to a new treatment arm; this is to protect the blind for subjects prior to the completion of the double- part of the study.

During the course of the study, the statistician and the programmers supporting the IDMC analysis will be unblinded and will remain separate from the wider project team throughout the life of the study. The randomization will be performed by the external IXRS provider, Almac. The blinded statistician supporting the study will have no access to the unblinded randomization schedule. The Investigator, the site personnel,

Version Date: 27-June-2024 Sponsor: Calliditas Therapeutics Suisse SA

Protocol No: GSN000350

the Sponsor and their representatives involved in monitoring and conducting the study, the Adjudication Committee, and the subjects will be blinded to treatment assignments until the study is unblinded for the primary analysis. For full details refer to the Data Blinding and Documentation plan.

8.3 Types of Planned Analysis

8.3.1 IDMC Analysis

The IDMC will oversee the safety of participating subjects. The IDMC will regularly review an aggregated list of events adjudicated by the Adjudication Committee. The IDMC will meet regularly over the life of the study for data review meetings as specified in the IDMC Charter. The IDMC may recommend change(s) to the setanaxib dose regimen(s), or interruption or discontinuation of an active treatment arm(s) based on the regular IDMC safety data reviews.

During the study there will be at least 2 planned data review meetings. The first IDMC data review meeting took place after approximately 20 subjects have been randomized and the second review meeting will take place after approximately 50 subjects have been randomized. The frequency or number of meetings can be modified, as necessary, by the Sponsor and/or the IDMC. Study enrollment will not be halted during planned IDMC review of safety data.

8.3.2 Interim Analysis (Not Applicable)

The interim analysis is no longer applicable for this revised Phase 2b study.

8.3.3 Primary Analysis

The data cut-off for the primary analysis will occur when 60-70 subjects randomized have had the opportunity to complete or discontinue from the 24-week double-blind treatment period.

The datasets extracted and cleaned for analysis will include all safety and efficacy data collected.

- The datasets prepared for primary analysis will encompass all safety and efficacy data gathered during this period.
- Data collected from 24-weeks to 52 weeks in the Main Part under protocol versions 1.0 to 4.0 will be descriptively summarized.
- Data collected during the extension phase under protocol versions 1.0 to 4.0 will be presented in listings only.

Once all outstanding data queries have been resolved or agreed as unresolvable after data cut-off and the analysis sets agreed, a soft lock of the database will occur when all week 24 data are available, and the primary analysis will be performed. Once all subjects have completed their end of treatment visit, a final hard lock of the database will occur, and no further updates can be made within the electronic data capture system.

9.0 Study Endpoints

9.1 Primary Efficacy Endpoint

The primary efficacy endpoint is the change in ALP (%) at Week 24 compared to Baseline.

9.2 Secondary Efficacy Endpoints

The secondary endpoints are:

- Change in fatigue at Week 24 compared to Baseline, as assessed by
 - The Patient-Reported Outcomes Measurement Information System (PROMIS)-short form-Fatigue 7b Daily

Sponsor: Calliditas Therapeutics Suisse SA

Protocol No: GSN000350

- o the Patient's Global Impression of Severity (PGIS) fatigue
- o the Patient's Global Impression of Change (PGIC) fatigue
- o the PBC-40 questionnaire (PBC-40) fatigue domain
- Change in liver stiffness at Week 24 compared to Screening, as assessed by transient elastography (FibroScan®)
- Change in ALP at Week 24 compared to Baseline, where setanaxib doses are combined
- Change in fatigue at Week 24 compared to Baseline, as assessed by the PROMIS short form-Fatigue 7b Daily, the PGIS fatigue, the PGIC fatigue, and the PBC-40 fatigue domain, where setanaxib doses are combined
- Change in liver stiffness at Week 24 compared to Screening, as assessed by transient elastography (FibroScan®), where setanaxib doses are combined
- Change in pruritus at Week 24 compared to Baseline, as assessed by the Worst Itch Numerical Rating Scale (WI-NRS), the PBC-40 itch domain, and the PGIS and the PGIC pruritus
- Changes in markers of cholestasis as assessed by proportion of subjects at Week 24 with:
 - ALP reduction to <1.67×ULN and total bilirubin ≤1xULN and a ≥15% or ≥30% or ≥40% or ≥70% ALP reduction from Baseline, respectively
 - ALP reduction to <1.5×ULN and total bilirubin ≤1xULN and with a ≥40% ALP reduction from Baseline
 - ALP<1xULN and total bilirubin ≤1xULN
 - Total bilirubin <0.6×ULN

9.3 Secondary Safety Endpoints

- AEs. Monitoring for AEs at all Visits
- AEs of special interest (AESIs):
 - Drug-induced liver injury (DILI)
 - o Anemia
 - Hypothyroidism
- Laboratory tests:
 - Hematology
 - o Biochemistry
 - Urinalysis
 - Thyroid function
- Vital Signs
- 12-lead electrocardiograms (ECGs): clinically significant abnormalities

Sponsor: Calliditas Therapeutics Suisse SA

Protocol No: GSN000350

9.4 Exploratory Endpoints

- Changes in markers of liver fibrosis, as assessed by Enhanced Liver Fibrosis (ELF) score, PRO-C3 (released N-terminal propeptide of Type III collagen), C3M (a peptide of helical collagen Type III degradation), and PRO-C3/C3M ratio at Week 24 compared to Baseline
- Changes in total and conjugated bilirubin over 24 weeks compared to Baseline
- Changes in markers of bile acid metabolism, as assessed by total bile acids, C4 (C4=7α-OH-4-cholesten-3-one), fibroblast growth factor (FGF)19, and FGF21 over 24 weeks compared to Baseline
- Changes in markers of liver function over 24 weeks compared to Baseline, as assessed by:
 - o Serum fibrinogen, albumin, and international normalized ratio (INR)
 - Alanine aminotransferase (ALT), aspartate aminotransferase (AST), gamma glutamyl transpeptidase (GGT), high sensitivity C-reactive protein (hsCRP), and immunoglobulin M (IgM) indicating liver inflammation and injury
- Assessment over a 24-week period of:
 - All-cause mortality
 - Proportion of subjects requiring a liver transplant (transplant list inclusion)
 - Proportion of subjects with a Model for End Stage Liver Disease (MELD) score of ≥15
 - Proportion of subjects with new onset of variceal/portal hypertension bleed and/or hepatic encephalopathy (West Haven criteria), spontaneous bacterial peritonitis, and ascites requiring treatment
- Change over a 24-week period compared to Baseline in:
 - Social isolation symptoms, as assessed by the PBC-40 social domain
 - o Overall health-related quality of life, as assessed by the PROMIS-29 questionnaire
 - EuroQol 5-dimension (EQ-5D) Utility Index
- Predose plasma concentrations of setanaxib and GKT138184 over a 24-week period

Secondary and exploratory endpoints captured for subjects who entered the extension phase under protocol versions 1.0 to 4.0 are described in protocol V4.0.

Sponsor: Calliditas Therapeutics Suisse SA

Protocol No: GSN000350

9.5 Estimand Attributes

The primary and secondary estimands are described in section 12.5.2.

9.6 Analysis Sets

9.6.1 All Enrolled Analysis Set

The All Enrolled analysis set (ENRL) consists of all subjects who signed informed consent for this study. The ENRL set will be used for summaries of disposition data.

9.6.2 Safety Analysis Set

The safety analysis set (SS) will include all randomized subjects who receive at least 1 tablet of IMP or placebo. Subjects included will be analyzed based on actual treatment initially received.

Safety data collected from subjects who entered the extension phase will be listed only.

9.6.3 Full Analysis Sets

The Full Analysis Set (FAS) will include all subjects who receive at least 1 tablet of IMP or placebo during the randomized part and have at least 1 post-baseline ALP value for the primary endpoint. Subjects included will be analyzed based on the treatment group they were randomized to regardless of the actual treatment received.

The FAS will be used for summaries of baseline data, efficacy data, and markers of liver fibrosis. Efficacy data collected from subjects who entered the extension phase will be listed only.

9.6.4 Per Protocol Analysis Set

Per Protocol analysis set (PPS) comprises of all subjects in the FAS who do not have any important protocol deviations during the 24-week treatment period that would potentially affect the efficacy of the study drug. Subjects will be analyzed based on the treatment group they were randomized to regardless of the actual treatment received.

Important protocol deviations are defined in the Protocol Deviation Guidance Document for the study. Prior to database lock and unblinding of the study, a blinded data review of the important protocol deviations (including programmatically determined deviations) will be performed to identify the important deviations impacting on the efficacy endpoints. This analysis set will be defined in a blinded manner prior to unblinding the study and agreed with Sponsor.

Deviations impacting efficacy that may lead to exclusion from the PPS will include:

- Deviations related to inclusion/exclusion criteria
- Incorrect treatment received (i.e. the actual treatment received is different to the initially randomized treatment at any point during the first 24-weeks of treatment)
- Non-compliance with study drug intake (≤80%) during the first 24-weeks of treatment
- Efficacy assessments at Week 24 performed significantly out of the protocol specified window
- Missing baseline data for the primary endpoint
- Use of prohibited concomitant medication that could have impacted the efficacy of study treatment.

9.6.5 PK Analysis Set (PKS)

PKS includes all subjects who receive at least 1 dose of setanaxib and have at least 1 measured concentration at a scheduled PK time point post-dose. Subjects may be excluded if they have an important AE or protocol deviations that may affect PK.

Version Date: 27-June-2024

Sponsor: Calliditas Therapeutics Suisse SA

Protocol No: GSN000350

10.0 Conventions and Derivations

10.1 Baseline and Change from Baseline

10.1.1 Baseline Values for Liver Biochemistry

Baseline values for liver biochemistry (ALP, ALT, AST, total and direct bilirubin, and GGT) are determined by the geometric mean of the last (up to) 3 measurements preceding the first administration of study drug. This includes unscheduled and screening visits. The formula for the geometric mean (GM) given three measurements a, b, and c is expressed as follows:

$$GM = \exp(\log(a) + \log(b) + \log(c)/3)$$

For subjects who have records for both Screening/Visit 1 and Baseline Visit 3, the baseline will be calculated as the geometric mean of these two values. If there is an additional unscheduled pre-dose result, the geometric mean will be calculated using up to three values.

For subjects who have records for Screening/Visit 1, Screening/Visit 2, and Baseline Visit 3, the Screening/Visit 1 result should be disregarded due to the subject's re-screening. The baseline should be calculated as the geometric mean of the Screening/Visit 2 and Baseline Visit 3 results. If there is an additional unscheduled pre-dose result, the geometric mean should include up to three values.

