12.5.2.1 Primary Analysis

Change in ALP at each scheduled timepoint up to Week 24 will be explored via tabulation and graphs for the FAS. Counts for the number of subjects that have a ≥15%, ≥30%, ≥40%, ≥50% and ≥70% reductions in ALP from baseline will be presented (these counts will be cumulative i.e a subject with ≥30% reduction at Week 24 will be counted in both ≥15% and ≥30% categories. Summary statistics for each schedule timepoints will be presented. These will include the geometric mean, geometric mean +/- geometric

Version Date: 27-June-2024

Sponsor: Calliditas Therapeutics Suisse SA

Protocol No: GSN000350

standard deviation, median, minimum, maximum. Baseline will be summarized in two ways – including all baseline data and baseline recalculated for subjects with evaluable Week 24 results (i.e. the subset of patients who have both baseline and week 24 ALP results).

In order to summarize % change at each scheduled timepoint, the ratio of ALP to baseline will be calculate for each scheduled timepoint and a logarithmic transformation applied. The mean and mean +/- standard deviation and mean +/- standard error of the log ratios will be calculated. The results will be backtransformed to get the geometric mean ratio (+/- geometric standard deviation and +/- geometric SE).

These results will be converted to the % scale and plotted as a line graph for each treatment group. ALP values after initiation of PBC-related medication will be treated as missing values at the analysis visit following initiation of the medication.

For the primary analysis, the ratio of ALP at week 24 to baseline will be log-transformed, as will ALP data from other timepoints used in the model. This will be analyzed using a Mixed Model Repeated Measures (MMRM) analysis based on the FAS and incorporating ALP data from baseline, weeks 2,4,8,12 and 24. Baseline ALP will be included as a covariate and will be calculated as the geometric mean of prerandomization ALP results, as defined in section 10.1 and log-transformed prior to inclusion in the analysis model. The model will also include terms for treatment group, visit, log(baseline) by visit, and visit by treatment group interaction. Subject will be included as a random effect.

the Mixed Model Repeated Measures (MMRM) model can be mathematically represented as follows:

$$Y_{ij} = \beta_0 + \beta_1$$

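### SAP 10.1.1 prints a three-value geometric-mean formula that divides only the last log by 3, contradicting the baseline rule stated in words

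*SAP*

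**What the plan says.** SAP 10.1.1 covers several analytes: "Baseline values for liver biochemistry (ALP, ALT, AST, total and direct bilirubin, and GGT"). Their baselines "are determined by the geometric mean of the last (up to) 3 measurements preceding the first administration of study drug". A formula follows, introduced by "The formula for the geometric mean (GM) given three measurements a, b, and c is expressed as follows". It reads exp(log(a) + log(b) + log(c)/3).

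The section then deals with the cases that will occur. With a Screening Visit 1 and a Day 1 value, "the baseline will be calculated as the geometric mean of these two values". After a retest at Screening Visit 2, Visit 1 is dropped and Visit 2 is averaged with Day 1, which again gives two values. A third value enters only when there is an extra unscheduled pre-dose result.

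SAP 12.5.2.1 uses this baseline twice in the primary model. It is the denominator of the response: "For the primary analysis, the ratio of ALP at week 24 to baseline will be log-transformed". It is also the covariate: "Baseline ALP will be included as a covariate and will be calculated as the geometric mean of prerandomization ALP results, as defined in section 10.1". The multiple-imputation sensitivity analysis in SAP 12.5.2.2.1 points to the same definition.

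**The concern.** The words and the formula in SAP 10.1.1 give different quantities. The words ask for a geometric mean. In the formula no bracket encloses the sum of the logs, so only the third log is divided by 3.

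SAP 10.1.1 is the rule from which baseline ALP is derived. If the printed line were programmed for a subject with three qualifying readings, that subject would have:

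- a wrong log ratio at every post-baseline visit;
- a wrong value of the log(baseline) covariate;
- a wrong result on each percentage-reduction threshold.

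The same section governs ALT and AST, so the summary in SAP 12.6.3 of values above twice baseline would be wrong for such a subject as well.

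**Working it through.** **Inputs.** The formula and the wording come from SAP 10.1.1. The design effect and the 16 evaluable subjects per arm come from SAP 8.1. The ALP readings are illustrative, because the documents contain no patient data. The plan gives no worked example of its own to reproduce.

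**Step 1: what the printed formula means.** By operator precedence,

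exp(log a + log b + (log c)/3) = a × b × c^(1/3).

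The geometric mean is

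exp[(log a + log b + log c)/3] = (a × b × c)^(1/3).

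The ratio of the first to the second is (a × b)^(2/3). It equals 1 only when a × b = 1.

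**Step 2: numbers.**

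| Readings (a, b, c) | As printed | Geometric mean | Ratio |
|---|---|---|---|
| 300, 300, 300 U/L | 602,490 | 300.0 | 2008 |
| 280, 300, 320 U/L | 574,552 | 299.55 | 1918 |
| 3, 3, 3 × ULN | 12.98 | 3.00 | 4.33 |
| 1.67, 1.67, 1.67 × ULN | 3.31 | 1.67 | 1.98 |

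First row by hand: 300 × 300 × 300^(1/3) = 90,000 × 6.694 = 602,490.

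**Step 3: two properties that no mean has.** The result depends on order: (280, 300, 320) gives 574,552 and (320, 300, 280) gives 628,045. It also depends on the unit, as the U/L and × ULN rows show.

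**Step 4: effect on one such subject.** Take three readings of 300 U/L.

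- Unchanged ALP of 300 at Week 24: 100 × (602,490 − 300)/602,490 = a 99.95% reduction. The subject would enter every stand-alone reduction count in SAP 12.5.2.1, up to the 70% threshold.
- True 25% fall, to 225: 100 × (602,490 − 225)/602,490 = a 99.96% reduction.
- Log scale: the log ratio moves by −ln(2008) ≈ −7.6 and the covariate by +7.6. The design effect in SAP 8.1 is ln(0.75/0.975) = −0.262, so the shift is about 7.6/0.262 = 29 times as large.
- Descriptive summary: one such subject among 16 evaluable in an arm would move the mean log ratio by −7.6/16 = −0.475. The reported geometric mean ratio would be multiplied by exp(−0.475) = 0.62.

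This last figure should not be read as a shift in the model's treatment contrast. The same log(baseline) is subtracted in the response and fitted by visit as a covariate. The Week 24 contrast is therefore equivalent to one from a model for log(ALP) with one badly distorted covariate value. How far it would move depends on the data and cannot be derived from the documents.

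**Step 5: who is reached.** The formula is stated for three measurements. The standard cases in SAP 10.1.1 use two values, and their rule is complete in words: for readings x and y it is the square root of x × y. Only subjects with an additional unscheduled pre-dose result have three. The documents do not say how many there are.

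**The case against.** **The words settle the meaning.** SAP 10.1.1 says geometric mean repeatedly, SAP 12.5.2.1 and 12.5.2.2.1 repeat it, and the term has one definition. On this view the line is a bracketing slip and not a rival definition. That stands, and it is the main reason the risk is low. It does not make the printed formula correct.

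**Someone would notice.** Baseline ALP is tabulated (SAP 12.2 and 12.5.2.1) and individual ALP profiles are plotted (SAP Table 7). The SAP change history records updates after two dry runs. A baseline near 600,000 U/L would be hard to miss. This also stands as a point about likelihood, although it does not show what was programmed.

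**The bracket may have been lost in reading the PDF.** Other expressions in the SAP are damaged: the Study Day formulas in 10.2 and the imputation expression in 10.17 are missing. Here, however, the brackets balance, and the stacked fractions in 10.1.5 and 12.3.3 came through intact. A loss is possible but nothing points to one; a look at the source file would settle it.

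**Stronger readings that the documents do not support.** A reader might infer that every baseline is wrong. The formula is limited to three measurements and most baselines should rest on two. A reader might call the absence of a two-value formula an error, but the two-value rule is fully defined in words. A reader might also think that all the responder criteria are affected. The limits relative to ULN for ALP and bilirubin in SAP 12.5.4.1 do not use baseline; only the percentage-reduction parts do.

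**Conclusion.** The concern holds in a limited form. The printed three-value formula equals a × b × c^(1/3) and contradicts the geometric mean it is said to express, within the section that defines baseline ALP for the primary endpoint. For readings near 300 U/L a literal implementation would inflate baseline about 2000-fold. It would affect only subjects with three qualifying readings, a number the documents do not give.

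The conclusion assumes that the formula in the source file matches the text available and that the illustrative readings are of a realistic order. Nothing in the documents shows that the analysis was programmed this way, and a reader should not infer that it was. The practical risk is low. The correction is still worth making, because this is an operative derivation for the primary variable and the change costs almost nothing.

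**What to change.** In SAP 10.1.1, replace the formula with GM = exp[(1/n) × sum of log(x_i)], where n is the number of qualifying pre-dose values (1 to 3). The general form is safer than adding one pair of brackets. A fixed divisor of 3 carried over to two readings of 300 U/L would give 300^(2/3), about 45.

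Then confirm that the programmed derivation matches, by checking the subjects with three qualifying values for each analyte in that section. The cost is one line of the SAP and a short programming check. Nothing in the design, data collection or sample size changes.

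One related matter stays open after this correction. Protocol 8.1 specifies an arithmetic mean for baseline ALP, and SAP 6.1 does not list the move to a geometric mean among its changes from the protocol. That needs its own reconciliation.
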